**Table 2: Maintenance Period Re-Randomized Group Assignments**

Group	Treatment	Dose	Week(s)	Route	Schedule
1A	Nemolizumab (CD14152)	30 mg	16, 20, 24, 28, 32, 36, 40, 44	sc	Q4W
1B	Nemolizumab (CD14152)	30 mg	16, 20*, 24, 28*, 32, 36*, 40, 44*	sc	Q8W*
1C	Placebo	Placebo	16, 20, 24, 28, 32, 36, 40, 44	sc	Q4W

*\*with placebo Q4W at Week 20, 28, 36, and 44 to maintain blind*

Abbreviation(s): Q4W=every 4 weeks; Q8W=every 8 weeks; sc=subcutaneous.

Beginning at Week 16, subjects in group 1A will receive active (ie, nemolizumab [CD14152]) study drug injections Q4W up to Week 44. Subjects in group 1B will receive active study drug injections Q8W, with placebo at alternating visits to maintain the blind. Group 1B subjects will receive the last active study drug injection at Week 40 (final injection at Week 44 will be placebo). Group 1C subjects will receive placebo Q4W (ie, through Week 44).

Subjects should continue the same background topical therapy used in the initial treatment period leading up to the Week 16 visit, including tapering or complete cessation (no use), if applicable. Throughout the maintenance period, adjustments to background topical therapy, as determined by the investigator, are permitted based on the subject's clinical response.

**Primary maintenance effect will be evaluated based on Week 48 assessments.** All maintenance endpoints will be analyzed independently from each pivotal study and by using pooled data after the completion of both trials.

CONFIDENTIAL

Subjects requiring rescue therapy before the Week 32 visit must undergo a required wait period (with continued study visits) until the Week 32 visit, at which time they may be considered for LTE eligibility/participation. Thereafter, no wait period is required.

Subjects who complete the Week 48 visit may be eligible to enroll into the LTE study (Protocol 118163). Subjects requiring rescue medication before the Week 48 visit may be considered for LTE eligibility. The follow-up visit is not required for subjects who participate in the LTE study.

Subjects who decline or are not eligible for the LTE study will be asked to complete the follow-up visit.

Subjects who discontinue the maintenance period prematurely should complete an ET visit and a follow-up visit 12 weeks after the last study drug injection.

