**Statistical Analysis:**

Principal Statistical Method

*Populations:* The intent-to-treat (ITT) population will consist of all randomized subjects. The safety population will include all randomized subjects who receive at least 1 dose of study drug. The ITT population will be the primary population for all efficacy analyses, and all safety data will be summarized based on the safety population.

CONFIDENTIAL

*Primary Endpoint:*

The 2 co-primary endpoints will be analyzed using a Cochran-Mantel-Haenszel test adjusted for randomized stratification variables (IGA severity and PP NRS).

*Key Secondary Endpoints:*

All key secondary endpoints will be analyzed similar to the analysis of primary endpoint using a stratified Cochran-Mantel-Haenszel test.

*Secondary Endpoints during Initial Period*

Binary endpoints will be analysed with the same method as primary endpoint using non-responder imputation.

Continuous and QoL endpoints will be analyzed using an analysis of covariance (ANCOVA) including treatment group and randomization stratification factors as factors and appropriate baseline values as a covariate, if applicable. Missing values will be imputed using MI under MAR assumption. In addition, EASI, PP NRS, CCI will be analyzed using a mixed-effect model for repeated measures (MMRM) approach, including terms of treatment group, stratification factors, and appropriate baseline values. An unstructured covariance will be used to model the within-patient errors in the analysis. A linear contrast will be used, within the MMRM framework, to estimate difference between nemolizumab and placebo. Treatment difference between nemolizumab and placebo will be estimated along with associated 95% confidence intervals.

*Secondary Endpoints during Maintenance Period*

All secondary endpoints during the maintenance period will be descriptively summarized.

*Multiplicity Adjustment:*

The primary comparison of interest is nemolizumab 30 mg compared to placebo for the co-primary endpoints in both populations (baseline PP NRS  $\geq 4$ ; baseline PP NRS  $\geq 7$ ).

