## 6.5 Dose Selection Rationale

Based on the outcome of the phase 2b dose-ranging study in adults, the 30-mg dose (with 60-mg loading dose), when administered Q4W, provided the best benefit/risk ratio of the 3 doses evaluated and is therefore selected as the final dose to be developed for the treatment of AD. Across the full range of subject body weights in the phase 2b study, the 30-mg dose (with 60-mg loading dose) provided a comparable observed exposure with respect to the body weight-based dose of 0.5 mg/kg tested during the phase 2a study.

Adolescent subjects will be enrolled after the sponsor confirms the safety of the 30-mg Q4W dose in adolescents in a separate clinical study (Protocol 116912).

The current study includes a 32-week maintenance period whereby clinical responders on nemolizumab 30 mg Q4W at Week 16 will be re-randomized (1:1:1) to 30 mg Q4W, 30 mg Q8W, or placebo to evaluate maintenance of effect. The nemolizumab 30 mg Q8W regimen is proposed to evaluate whether a clinical response can be maintained with a lower dosing frequency.

PK/pharmacodynamic (PD) modeling was performed on three clinical endpoints (EASI, IGA, and PP NRS) to support selection of the additional Q8W dose regimen for Phase 3 maintenance. The medians of the active treatment arms were not contained within the range of the placebo for all clinical endpoints, indicating a benefit with active treatment over placebo in both dose regimens (Q4W and Q8W). While higher efficacy on all clinical endpoints was observed with the Q4W dose regimen, it was evidenced that subcutaneous nemolizumab Q8W for 16 weeks will maintain clinical benefit compared to placebo.

PK/PD modeling provides the rationale to evaluate and compare the safety and efficacy of Q4W and Q8W dosing of 30 mg nemolizumab in the maintenance phase of the pivotal studies.

CONFIDENTIAL

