The study includes a 16-week initial treatment period, a 32-week maintenance period, and an 8-week follow-up period (ie, 12 weeks after last study drug administration) for subjects who decline or are not eligible to enter the LTE study. A 16-week treatment is considered adequate to evaluate the safety and efficacy of nemolizumab based on the results of the phase 2b study (114322) and other registrational studies for the treatment of AD. The maintenance period will compare the maintenance of effect of 2 nemolizumab dosing regimens (30 mg Q4W and 30 mg Q8W) compared to placebo. The nemolizumab 30 mg Q8W regimen is proposed to evaluate whether a clinical response can be maintained with a lower dosing frequency. Subjects who are clinical responders at Week 16 will be re-randomized (1:1:1) to 1 of 3 maintenance treatment groups.

CONFIDENTIAL

Clinical responders are defined as:

- IGA of 0 (clear) or 1 (almost clear) at Week 16
- OR**
- EASI-75 at Week 16

Subjects who are non-responders at the Week 16 visit can be considered for LTE study eligibility. All subjects who complete the maintenance period (Week 48 visit) can be considered for LTE study eligibility.

The selected endpoints for assessing the PK and safety of nemolizumab (CD14152) are in accordance with current standards, as are the safety endpoints of the trial. Blinding subjects and the designated study team to the treatment assignment(s) ensures objectivity and minimizes bias. Randomization through the interactive response technology (IRT) guards against selection bias.

A follow-up visit is scheduled for subjects who decline participation in the LTE study or are not eligible to participate. The duration of the follow-up period from the final nemolizumab dose (12 weeks) corresponds to approximately 5 half-lives of nemolizumab, which is considered adequate to ensure subject safety. The follow-up visit is not required for subjects who participate in the LTE study as its primary objective is long-term evaluation of safety.

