This document is confidential.

means, estimated standard error, and 95% CI for each endpoint will be presented for each treatment group and scheduled analysis visit. The estimated treatment difference for each endpoint at each visit will be summarized by presenting the difference in least squares means between treatment groups, the two-sided 95% CI, and associated p-value. CCI

[Redacted text block]

Table 10-1 Analysis Methods

Continuous/QoL Endpoints in Initial Period	Analysis Method
EASI	ANCOVA using MI-MAR, MMRM
PP NRS	ANCOVA using MI-MAR, MMRM

CCI [Redacted text block]

All efficacy endpoints of the Initial Period will be summarized by treatment and analysis visit.

Secondary Endpoints During Maintenance Period:

All secondary endpoints of the Maintenance Period will be descriptively summarized by treatment group at each analysis visit for the ITT population.

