IGA will be summarized as a categorical and continuous variable at each analysis visit. Absolute change from Baseline and from Week 16 will be also presented in the summary for the ITT population.

IGA success will be calculated using Baseline and Maintenance Baseline (Week 16) as the reference point for change on the IGA scale. The proportion of subjects with IGA success will be summarized using OC, Non-responder and LOCF.

Line plot for proportion of subject with IGA success from Baseline using Non-responder imputation will be presented for Maintenance Period on the ITT population.

For the subset of subjects achieving IGA success at Week 16, the proportion of subjects maintaining IGA success at each visit throughout the Maintenance Period will be summarized. 'Maintaining IGA success'

This document is confidential.

is defined if achieved IGA success at every analysis visit until the analysis visit summarized. For example, if a subject achieved IGA success until Week 28 except Week 24, this subject will not be counted as 'Subjects maintained IGA success' at Week 28.

The number and percentage of subjects who achieved IGA success and an improvement of PP NRS ≥ 4 from Week 16 will be summarized for the ITT population using OC and for the subset of subjects with such a response at Week 16.

No hypothesis testing will be performed for Maintenance Period.

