For the subset of patients achieving EASI-75 at Week 16, the proportion of subjects maintaining EASI-75 at each visit throughout the Maintenance Period will be summarized. 'Maintaining EASI-75' is defined if a subject achieved EASI-75 at every analysis visits until the analysis visit summarized. For example, if a subject achieved EASI-75 until Week 28 except Week 24 then this subject will not be considered as "Subject maintaining EASI-75" at Week 28.

The number and percentage of subjects who achieved EASI-75 and an improvement of PP NRS ≥ 4 from Week 16 will be summarized for the ITT population using OC and for the subset of subjects with such a response at Week 16.

Individual components of the EASI score will be summarized as continuous variables. Change in individual components of the EASI score at each analysis visit from Week 16 to Week 48 will also be summarized.

This document is confidential.

No hypothesis testing will be performed.

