10.3.24. Relapse during Maintenance Period

[figure not shown]
Relapse is defined as worsening of AD requiring rescue therapy, if judged to be medically necessary by the investigator (i.e., clinically significant worsening of signs and/or symptoms of AD). Relapse will be determine using AE, PR and CM data.

The number and percentage of subjects with relapse (worsening of AD requiring rescue therapy) will be summarized for the Maintenance Period using OC.

In addition, the time to first relapse from Week 16 will be calculated during the Maintenance Period using Kaplan-Meier methodology by presenting the point estimates of the quartiles estimates with the corresponding 95% CI. Subjects without such an event during Maintenance Period will be censored for the analysis and date of last visit of Maintenance Period will be used as the censoring date. Subjects who discontinued during Maintenance Period without relapse will also be censored as described above. Kaplan-Meier curve will also be provided.

This document is confidential.

CCI

[figure not shown]
1.0

CD14152.SPR118169.SAP.V01

Approved 10-Nov-2022 00:00:00

This document is confidential.

CCI

1.0

CD14152.SPR118169.SAP.V01

Approved 10-Nov-2022 00:00:00

This document is confidential.

13. Safety

All safety data will be summarized and listed on the Safety population.

Safety assessments will be conducted for all subjects at the screening visit (upon signing of the ICF) and at every subsequent visit. Safety will be assessed on the basis of AEs, unexpected adverse reactions, clinical laboratory data, vital signs, physical examination, respiratory examination, and ECG parameters. Summary of all safety endpoints will be presented by study Period (Initial Period, Maintenance Period, and Follow-up Period) for each treatment group.

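### The protocol says the re-randomised maintenance period will compare Q4W and Q8W with placebo, but neither document's visible analysis text plans a between-arm difference or an interval for one

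*SAP*

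**What the plan says.** **Comparative aim.** Protocol Section 8.2.1: "The maintenance period will compare the maintenance of effect of 2 nemolizumab dosing regimens (30 mg Q4W and 30 mg Q8W) compared to placebo". Protocol Section 6.5, on the choice of regimens: "PK/PD modeling provides the rationale to evaluate and compare the safety and efficacy of Q4W and Q8W dosing of 30 mg nemolizumab". The same section explains that Q8W is included to see whether response holds with less frequent dosing. The synopsis, below Table 2, fixes the time point: "Primary maintenance effect will be evaluated based on Week 48 assessments". Section 8.1 repeats this. Both places add that maintenance endpoints will be analysed by study and also pooled over two pivotal trials.

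**Planned analysis.** Protocol synopsis, Statistical Analysis: "All secondary endpoints during the maintenance period will be descriptively summarized". SAP Section 10.3: "All secondary endpoints of the Maintenance Period will be descriptively summarized by treatment group at each analysis visit for the ITT population". SAP Section 10.3.1 adds, for IGA: "No hypothesis testing will be performed for Maintenance Period". Sections 10.3.2 (EASI) and 10.3.3 (pruritus NRS) also exclude testing.

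**Intervals that are planned.** For time to first relapse, SAP Section 10.3.24 estimates each arm "using Kaplan-Meier methodology by presenting the point estimates of the quartiles estimates with the corresponding 95% CI". In the initial period, by contrast, SAP Sections 10.1.1, 10.3.1 and 10.3.2 plan unadjusted and strata-adjusted treatment differences with confidence intervals.

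**The concern.** Re-randomising responders 1:1:1 gives unbiased contrasts between continuing at Q4W, spacing to Q8W and withdrawing to placebo. That is the reason for the design, and the protocol says as much. Yet the tables will show a percentage for each arm, and readers will subtract one from another without being told how precise the result is. The Q4W-Q8W gap matters most here, because it bears on dosing frequency and is likely to be the smallest. A modest gap could be read as a real loss of response, or a small one as equivalence, when the data support neither.

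A second problem is choice after the fact. SAP Section 10.3.1 summarises maintenance IGA success under three data rules (observed cases, non-responder, LOCF) and against two reference points (initial baseline and Week 16), and does not name one combination as the main one. If a difference is later quoted, it can be picked with the results in view.

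**Working it through.** **1. Number per arm, from the plan's own figure.** Inputs from the protocol synopsis: 750 randomised 2:1 (500 and 250), 15% dropout, and responder rates of 45% on active and 12% on placebo.
- Nemolizumab: 500 × 0.85 × 0.45 = 191.25 (stated 190).
- Placebo: 250 × 0.85 × 0.12 = 25.5 (stated 26).
- Total: 216.75 (stated about 216).

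The stated figures reproduce. Re-randomised 1:1:1, 190/3 gives about 63 per arm. The 26 initial-placebo responders are not re-randomised, and SAP Section 6.1 leaves them out of the maintenance ITT set. The placebo arm in any contrast is therefore group 1C.

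**2. Precision of a Week 48 difference.** The documents give no Week 48 response rates, so a range is assumed. The 95% half-width is 1.96 × √[(p₁(1−p₁) + p₂(1−p₂))/n].

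| Assumed rates | n = 63 per arm | n = 126 per arm |
|---|---|---|
| 50% vs 50% | 17.5 points | 12.3 |
| 70% vs 50% | 16.7 | 11.8 |
| 80% vs 50% | 15.8 | 11.2 |
| 80% vs 70% | 15.0 | 10.6 |
| 90% vs 80% | 12.3 | 8.7 |

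First row: 1.96 × √(0.50/63) = 0.175. Last row: 1.96 × √(0.25/63) = 0.123. The right-hand column assumes a second pivotal trial of the same size, which the documents do not state.

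**3. What testing would offer.** Power at two-sided 5% is Φ[(|p₁−p₂| − 1.96·se₀)/se₁], where se₀ uses the pooled rate and se₁ the separate rates. With 63 per arm it is 95% for 80% vs 50%, 63% for 70% vs 50%, and 25% for 80% vs 70%. One study can show a large withdrawal effect but not a modest gap between regimens, so intervals suit this period better than tests.

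**4. Search of the visible text.** SAP Section 8.1 summarises categorical variables as frequencies and percentages. The maintenance parts of Sections 10.3.1 to 10.3.3 follow the general sentence in Section 10.3. Section 10.3.24 and the rescue-therapy summary before it give within-arm Kaplan-Meier estimates. None of them specifies a difference, a contrast or an interval for one.

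**The case against.** The descriptive plan is consistent and looks deliberate. The protocol states no maintenance hypothesis, power or alpha. The secondary objective is to evaluate maintenance treatment, and its wording does not itself demand a comparison. With n/N in each arm, a reader can compute an unadjusted interval. A pooled analysis is planned, but its plan is not among these documents. The lists of maintenance endpoints and parts of SAP Section 10.3 are blacked out, so a contrast could sit there.

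Much of this stands. A reader might infer that the SAP dropped a comparison the protocol's statistics had promised. It did not: the protocol synopsis already says descriptive, and the SAP follows it. A reader might also infer that the period has no measure of uncertainty at all. That too is unsupported, since within-arm Kaplan-Meier intervals and standard deviations for continuous summaries are planned.

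The objection does not remove the gap. Estimating a difference is not a hypothesis test and spends no alpha. Reader arithmetic cannot recover a strata-adjusted difference from arm totals, and it does not settle which data rule and reference point apply. The redactions leave some doubt, but the general sentence in Section 10.3 covers all maintenance secondary endpoints and every visible subsection agrees with it.

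**Conclusion.** The point holds as a mismatch between a stated comparative aim (Protocol Sections 6.5 and 8.2.1) and a descriptive analysis in both documents. What is missing is a between-arm estimate with its interval; no figure in the plan is wrong, and the co-primary analyses are unaffected. The interval would be about ±12 to ±18 points per study, and about ±9 to ±12 pooled. This rests on 63 per arm, assumed Week 48 rates between 50% vs 50% and 90% vs 80%, and an equal-sized second trial for the pooled figure.

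Two further inferences should be resisted. One is a fixed number of points below which any gap is noise: the half-width moves with the response rates, so no single threshold follows. The other is that hazard ratios for relapse are needed. They would bring in a proportional-hazards assumption that is doubtful when withdrawal follows a drug with a half-life of about two weeks (Protocol Section 6.2.1), and relapse is itself defined by rescue use.

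**What to change.** In SAP Section 10.3, and in the matching sentence of the protocol synopsis, pre-specify the following for Week 48.

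- **Endpoints:** IGA success and EASI-75, both relative to the initial baseline. Someone entering maintenance at IGA 0 or 1 cannot fall a further 2 points, so Week 16 cannot serve as the reference for IGA success. The designated maintenance endpoints are redacted; if they differ, apply the same rule to them.
- **Data rule:** rescue use or missing data counted as non-response.
- **Contrasts:** Q4W (1A) minus placebo (1C), Q8W (1B) minus placebo (1C), and Q4W minus Q8W.
- **Estimate:** risk difference with 95% confidence interval, adjusted for the baseline strata as in the initial period, with the unadjusted difference alongside. Protocol Section 8.4.5 does not say that re-randomisation was stratified, so both are worth showing.
- **Label:** estimation only, outside the alpha-controlled family, not adjusted for multiplicity.
- **Pooled analysis:** the same contrasts.

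The cost is a few columns in the Week 48 tables, using a method the SAP already contains. The small downside is that the intervals are unadjusted for multiplicity, which a footnote should state. If the sponsor prefers to stay purely descriptive, the comparative wording in Protocol Sections 6.5 and 8.2.1 should be softened to match, though the trial would then not report the contrast its design provides.

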10.3.1. Investigator’s Global Assessment (IGA)

The IGA is a 5-point scale ranging from 0 (clear) to 4 (severe) used by the investigator or trained designee to evaluate the global severity of AD and the clinical response to a treatment (see Table 10-2).

Table 10-2: Investigator Global Assessment Scale

This document is confidential.

Statistical Analysis Plan for Interventional Studies

Sponsor: Galderma Research & Development, LLC; Protocol No.: RD.06.SPR.118169

Status	Score	Definition
Clear	0	Minor, residual hypopigmentation/hyperpigmentation, no erythema or induration/papulation, no oozing/crusting.
Almost clear	1	Trace faint pink erythema, with barely perceptible induration/papulation and no oozing/crusting.
Mild	2	Faint pink erythema with mild induration/papulation and no oozing/crusting.
Moderate	3	Pink-red erythema with moderate induration/papulation with or without oozing/crusting.
Severe	4	Deep or bright red erythema with severe induration/papulation with oozing/crusting.

IGA success is defined as 0 (clear) or 1 (almost clear) on the IGA scale and a ≥ 2 -point reduction from Baseline.

During Initial Period:

IGA will be collected at Screening, Baseline, Week 4, Week 8, Week 12, Week 16 and Early termination of the Initial Period.

IGA will be summarized as a categorical and continuous variable at each analysis visit. Absolute change from Baseline for the IGA score will also be presented in the summary for ITT and PP population.

IGA success will be calculated using Initial Period Baseline as the reference point for change on the IGA scale. The proportion of subjects with IGA success (OC, non-responder, LOCF) will be summarized.

Line plot for proportion of subject with IGA success using Non-responder imputation will be presented for Initial Period on the ITT population.

The number and percentage of subjects with IGA success and the number and percentage of subjects who achieved IGA success and an improvement of PP NRS ≥ 4 from Baseline will be analyzed up to Week 12 for the ITT population using non-responder.

The estimate of treatment unadjusted and strata-adjusted differences with the corresponding 2-sided 95% confidence intervals, and p-values from the Cochran-Mantel-Haenszel test will be presented.

During Maintenance Period:

IGA will be collected at Week 20, Week 24, Week 28, Week 32, Week 36, Week 40, Week 44, Week 48 and Early termination of the Maintenance Period.

IGA will be summarized as a categorical and continuous variable at each analysis visit. Absolute change from Baseline and from Week 16 will be also presented in the summary for the ITT population.

IGA success will be calculated using Baseline and Maintenance Baseline (Week 16) as the reference point for change on the IGA scale. The proportion of subjects with IGA success will be summarized using OC, Non-responder and LOCF.

Line plot for proportion of subject with IGA success from Baseline using Non-responder imputation will be presented for Maintenance Period on the ITT population.

For the subset of subjects achieving IGA success at Week 16, the proportion of subjects maintaining IGA success at each visit throughout the Maintenance Period will be summarized. 'Maintaining IGA success'

This document is confidential.

is defined if achieved IGA success at every analysis visit until the analysis visit summarized. For example, if a subject achieved IGA success until Week 28 except Week 24, this subject will not be counted as 'Subjects maintained IGA success' at Week 28.

The number and percentage of subjects who achieved IGA success and an improvement of PP NRS ≥ 4 from Week 16 will be summarized for the ITT population using OC and for the subset of subjects with such a response at Week 16.

No hypothesis testing will be performed for Maintenance Period.

